- The informed consent process will be conducted by trained research staff and will include all aspects of the study and a full disclosure of the risks, benefits, procedures, and alternatives. The study consent and HIPAA authorization will be signed after all questions have been discussed and answered. Collection of baseline information, including such items as contact information, BP measurements, demographic and pregnancy history information, concomitant medications, and lifestyle information will follow the informed consent process.
- All data will be kept confidential to comply with HIPAA regulations. No
 patient identifiers will be included in the data sets. All data will be kept in a
 password protected folder within the ARMC network and will only be made

- available to study investigators. The database will be controlled, and password-protected.
- All data and records will be kept confidential in accordance with Institutional policies and HIPAA. There will be extremely limited access to subject information. All data will be anonymized before publication. Patient Data Sets will include identifiers that are strictly limited to medical record number, ethnicity, age and sex, along with associated clinical data. Patient Data Sets will be imported into password protected Excel files located in an encrypted folder accessible only to the investigators involved in the study, IRB, and IT on the ARMC server. All published poster presentations, abstracts and papers will be de-identified, with a medical record numbers and any other identifying material removed. Patient's age, parity, sex and race will be used in publication for educational purposes.

VI: Study Design and analysis:

- All patients admitted for term induction of labor will be asked to participate if they
 meet the inclusion criteria as described above. Once consented, the participants
 will be randomly allocated into two groups: control versus intervention group.
 Randomization will be done as block randomization based on maternal BMI at
 time of admission, all odd patients will be enrolled into the control group and all
 even study numbers will be in the intervention group.
 - -Control group: no medication

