 - -Intervention group: Calcium carbonate 500 mg 4 tablets PO x1 -Calcium carbonate (TUMS) is an over-the-counter antacid medication and common side effects include changes in bowel habits like constipation or diarrhea, bloating, gas, and abdominal discomfort. Rare side effects include allergic reactions and hypercalcemia if taken in large amounts. The daily recommended max dose is 8000mg, we will be giving a max of 2000 mg.⁷
- The primary outcome will determine the effect of calcium carbonate on uterine contraction strength, assessed by comparing Montevideo units (MVU), frequency of contractions, and peak of the contractions 30 minutes before medication administration and at 30 minutes interval for a total of 2 hours afterward. To ensure accuracy in MVU measurement, all patients should already have an intrauterine pressure catheter (IUPC) in place at the discretion of the OB provider before they are enrolled. Secondary outcomes include duration of first and second stage of labor, mode of delivery, neonatal outcomes (NICU admission, low APGAR scores), and maternal outcomes (PPH).
- Other maternal information such as height, weight, BMI, age, parity, race, gestational age, cervical dilation/effacement/station at the time of medication administration and after administration, time to delivery, oxytocin use, epidural use, Apgars, perineal laceration, QBL, birthweight, mode of delivery, delivery complications will be obtained to compare among the two groups to make sure there are no confounding factors. Since Pitocin dose is a confounding variable after receiving the medication, patients must be off Pitocin during study period.

- The data collected will be divided into 2 groups: control versus intervention group. Statistical analysis included descriptive statistics to summarize maternal characteristics and clinical outcomes. Normality testing was performed, and appropriate comparative statistical tests were selected, including two-way Student's t-tests, Tukey's tests, or post hoc Student–Newman–Keuls tests as appropriate. A p-value of less than 0.05 was considered statistically significant. Univariate and multivariate linear regression analyses were conducted to identify associations between maternal, fetal, and labor-related variables and study outcomes.
- Uni- and multivariate analysis with linear regression modeling will be used to identify significant associations between maternal, fetal, or labor characteristics.

VII: Risks and Benefits:

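### Admission BMI is named as the blocking factor, but no planned arm comparison includes it; the cost is a modest, conditional gain in precision forgone

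*Combined protocol and SAP*

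**What the plan says.** All the relevant text is in section VI (Study Design and analysis), apart from the sample size in section V (Methods, subject recruitment).

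- **Allocation.** "Randomization will be done as block randomization based on maternal BMI". The sentence goes on: "time of admission, all odd patients will be enrolled into the control group and all", with even study numbers going to the intervention. It gives no BMI categories, cut-points, block size or separate numbering by stratum.
- **Tests.** "Normality testing was performed, and appropriate comparative statistical tests were selected", "including two-way Student's t-tests, Tukey's tests, or post hoc Student–Newman–Keuls tests as appropriate". No covariate is named and no single primary test is designated.
- **Regression.** "Univariate and multivariate linear regression analyses were conducted to identify associations between maternal, fetal, and labor-related variables and study outcomes". Neither arm nor BMI is named as a model term, and the model is not said to estimate the arm effect.
- **Role of BMI in the analysis.** It appears in a list of data to be compared between groups as a check on confounding: "Other maternal information such as height, weight, BMI, age, parity, race, gestational age" and others.
- **Threshold.** "A p-value of less than 0.05 was considered statistically significant".
- **Sample size.** At least 40 women per group, for a 20% difference from a baseline of 200 Montevideo units (MVU) with 80% power. No SD and no allowance for BMI is given.

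**The concern.** When allocation is balanced on a covariate that predicts the outcome, the covariate's variation is largely removed from the difference between arms. A two-sample t-test still counts that variation in its standard error. The reported interval is then wider than the design warrants, the true type I error falls below 5%, and some achievable power is left unused. The usual remedy is to put the balancing factor into the analysis model.

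BMI is the only factor the plan names for allocation, and it will be recorded for every woman, yet the plan does not commit the arm comparison to using it. The choice of test is also left open until the data are seen. At stake is precision in a trial of 80 women. There is no risk of excess false positives from this source.

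**Working it through.** **1. The plan's own figure.** The target difference is 20% of 200, which is 40 MVU. The SD is missing, so 40 per arm can only be back-solved. I read "two-way Student's t-tests" as two-sided, which is an assumption:

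SD = 40 / [(1.960 + 0.842) × √(2/40)] = 40 / (2.802 × 0.2236) ≈ 63.9 MVU.

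With the exact t-test the SD is 63.1, an effect of 40/63.1 = 0.634 SD. So 80 women give 80% power with no BMI adjustment if the SD is about 63 to 64. The documents neither confirm nor refute that SD.

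**2. The missing input.** Let r be the correlation of BMI with the outcome. The documents give none, so I assume 0.2, 0.3 and 0.5. The residual SD after BMI is k × SD, with k = √(1 − r²) = 0.980, 0.954 and 0.866. I treat MVU as a single continuous value per woman.

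**3. Reading A: allocation balanced within BMI blocks.** The arm difference varies with SE reduced by the factor k, but the t-test uses the full SE. In large samples:

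- type I error of the t-test = 2[1 − Φ(1.96/k)]
- power of the t-test = Φ[(2.802 − 1.96)/k]
- power with BMI in the model = Φ(2.802/k − 1.96)

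The simulation used three BMI strata, blocks of two, 80 women and an effect of 0.634 SD.

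| r (assumed) | Type I, t-test: formula | Type I, t-test: simulated | Power, t-test v adjusted: formula | Power, t-test v adjusted: simulated |
|---|---|---|---|---|
| 0.2 | 4.5% | 4.3% | 80.5 v 81.6% | 80.0 v 81.0% |
| 0.3 | 4.0% | 4.2% | 81.1 v 83.6% | 81.4 v 83.8% |
| 0.5 | 2.4% | 2.7% | 83.4 v 89.9% | 82.6 v 89.8% |

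Repeat runs moved the simulated type I error by a few tenths of a point (4.3 to 4.7%, 4.2 to 4.3% and 2.5 to 2.8%). Odd/even numbering applied within BMI blocks gave much the same: 4.7%, 3.8% and 2.8%.

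On the back-solved SD, the 95% CI half-width is 1.96 × 63.9 × √(2/40) = 28.0 MVU unadjusted. Multiplying by k gives 27.4, 26.7 and 24.2 MVU adjusted.

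**4. Reading B: odd/even across all women, regardless of BMI.** BMI is not balanced by design, so the t-test's SE is correct. Simulated type I error was 5.3%, 4.8% and 4.8% at r = 0.2, 0.3 and 0.5. Adjustment still removes residual variance: simulated power rose from 80.0 to 83.2% at r = 0.3 and from 79.3 to 89.3% at r = 0.5. At r = 0.2 the formula gives 80.0 to 81.6%.

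**5. Gain forgone.**

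- Reading A, simulated: 81.0 − 80.0 = 1.0, 83.8 − 81.4 = 2.4 and 89.8 − 82.6 = 7.2 points.
- Reading B: 1.6 points (formula), then 83.2 − 80.0 = 3.2 and 89.3 − 79.3 = 10.0 points (simulated).

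**6. Degrees of freedom.** Continuous BMI costs one. Three strata add two more. An indicator for every block of two would cost 80/2 − 1 = 39, which should be avoided.

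**The case against.** The strongest reply is that the premise is not secure. The sentence that names BMI blocking also describes odd/even assignment, with no strata or cut-points. If study numbers simply run on, BMI is not balanced by design, and the mechanism that makes the t-test conservative is absent. This stands, and it is why the conclusion is conditional.

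A reader might infer that the error bars are too wide and that power bought by the design is lost. The documents support neither. Intervals that are too wide need both real BMI blocking and a BMI-outcome association, and the second is nowhere given. The sample size took no credit for BMI, and the unadjusted test keeps about 80% power or slightly more in every setting above. What is forgone is an extra.

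A reader might also infer that the plan has chosen an unadjusted t-test that ignores BMI. That too goes further than the text: several tests are listed and multivariate linear regression is planned. The supportable statement is that no arm comparison is specified that includes BMI.

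Two further points are fair. The error is in the conservative direction, and at r = 0.2 the gain is only 1 to 2 points. MVU before dosing is also measured and would be a natural covariate for the primary outcome, but that does not remove the case for BMI.

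**Conclusion.** The omission is clear from the text: the plan's one named allocation factor has no stated place in the estimate of the arm effect. Its consequence depends on two things the documents leave open. With true BMI blocks and a prognostic BMI, the t-test is conservative, with type I error of about 4.3% at r = 0.2, 4.2% at 0.3 and 2.7% at 0.5. With odd/even across all women, it is valid.

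Under either reading the planned 80% power is kept. The forgone gain is about 1 to 3 points at r = 0.2 to 0.3, and 7 to 10 points at r = 0.5, where BMI would explain 25% of the outcome variance. These sizes rest on assumed correlations, 40 women per arm, two-sided 5% and the effect back-solved from the sample size. This is a near-free improvement to the plan and not a threat to its validity.

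**What to change.** In section VI, first reconcile the BMI-blocking and odd/even statements: say whether BMI strata are used and, if so, give the cut-points, the block size and how numbers are assigned within strata. Then amend the analysis paragraph:

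- **MVU and the other continuous outcomes:** the primary comparison is a linear model with arm and admission BMI as a continuous covariate. Add the BMI stratum if strata are used, but not an indicator for each small block. Report the arm coefficient with its 95% CI.
- **Mode of delivery, NICU admission and postpartum hemorrhage:** a binary-outcome model with arm and BMI, where event counts allow.
- **Unadjusted test:** keep it as a sensitivity analysis.

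The cost is a few sentences, one degree of freedom for BMI plus one for each additional stratum, and no new data. The change does not repair the predictability of odd/even assignment, which needs its own correction.

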- Purpose of the Study: The purpose of the study is to investigate whether calcium carbonate supplementation during labor can improve uterine contractility and decrease labor dystocia. By conducting this trial, the aim is to provide evidencebased guidance to healthcare providers regarding the potential use of calcium carbonate as a preventive measure for labor dystocia.
- Hypothesis: We hypothesized that pregnant women, those who receive calcium carbonate supplementation will have improve uterine contractility and a shorter labor course.
- Alternative Hypothesis: Calcium supplementation will have no effect on contractility

IV: Study type: Randomized control trial

V: Methods:

Location: Labor and Delivery at Arrowhead Regional Medical Center

- Start: Plan to start at the receipt of IRB approval. We anticipate the duration of the study to be about 2 years.
- Type of research: other
- Inclusion:
- Patients undergoing induction of labor with an intrauterine pressure catheter already in place at the discretion of the OB provider
- Maternal age: >18 years of age
- Gestational age > 37 weeks 0 day
- Cephalic presentation
- Able to understand/read English and/or Spanish
- Exclusion:
 - Maternal age < 18 years of age
 - Incarcerated patients
 - Active labor
 - Active illicit substance use
 - Multiple fetal gestations
 - Bleeding concerning for hemorrhage/placental abruption/placenta previa, or other contraindications to vaginal delivery
 - Aneuploidy or fetal structural anomaly
 - Prior cesarean deliveries
 - Known maternal arrhythmias, hyperparathyroidism, heart failure, kidney failure, liver failure, and history of kidney stones
 - Medications that affect uterine contractility like Magnesium, Terbutaline, Cytotec (need to be 4 hours after administration to enroll)
- Subject recruitment: All women with a term pregnancy, admitted for induction of labor will be asked to participate if age >18 years of age and English/Spanish speaking. We will plan to recruit when a patient is at least 4 cm and greater with an IUPC already in place. Using a baseline Montevideo unit of 200, if we were to aim for a 20% difference with a power of 80%, a sample size of 80 would be the minimum goal to enroll. Therefore, our goal is to enroll at least 40 patients into each group.

Consent:

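### Allocation is labelled BMI-based block randomisation, but the only rule given is odd to control and even to intervention, which does not use BMI and may be predictable

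*Combined protocol and SAP*

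**What the plan says.** Section VI (Study Design and analysis) states that, after consent, participants "will be randomly allocated into two groups: control versus intervention group". It continues: "Randomization will be done as block randomization based on maternal BMI at" the time of admission. The same sentence then gives the assignment rule: "all odd patients will be enrolled into the control group and all" "even study numbers will be in the intervention group". Nothing further is said about how the sequence is produced, how BMI is categorised, what the block size is, how study numbers are issued, or how the next assignment is hidden. BMI appears again in section VI only as one of the maternal characteristics to be collected and compared between the groups.

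Three other statements bear on this:

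- The comparator is "Control group: no medication". No placebo or masking is described.
- Section V (Inclusion) requires an "intrauterine pressure catheter already in place at the discretion of the OB provider". Section VI repeats that "all patients should already have an intrauterine pressure catheter (IUPC) in place at the discretion of the OB provider before they are enrolled".
- Section VI opens with "All patients admitted for term induction of labor will be asked to participate if they" meet the criteria. Section V sets the recruitment point at a dilation of 4 cm or more with the catheter in place.

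The title and section IV both call the study a randomised controlled trial.

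**The concern.** The label and the rule describe different procedures. A block design based on BMI needs a random order within blocks and defined BMI groups. The parity of a study number supplies neither.

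If numbers are handed out in order of enrolment, the rule is alternation and the person recruiting knows the next arm before seeking consent. With an untreated control group, anyone who knows what the last woman received can also infer the next arm.

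This trial is more exposed than most because the primary outcome is uterine activity, and the catheter displays it before a woman is approached. Someone who knows the next arm could decide whether or when to approach her according to how she is contracting or progressing. Unlike an analysis choice, a foreseeable allocation cannot be repaired after the women are enrolled. A study run by the rule as written would be quasi-randomised.

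**Working it through.** **1. Possible readings of the rule.** The text does not say how numbers are issued, so each reading is an assumption.

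| How numbers are issued | Uses BMI? | Next arm foreseeable? |
|---|---|---|
| Consecutively over all women | No | Yes, 100% |
| Consecutively within BMI groups | Yes, arms differ by at most 1 woman per group | Yes |
| Parity only codes a hidden random list | Depends on the list | Depends on the list, which is not described |

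No reading makes the present sentence sufficient.

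**2. The plan's own figure.** Section V gives a baseline of 200 MVU, a 20% difference, 80% power and 80 women. The difference is 0.20 × 200 = 40 MVU. No SD is stated, so the sample size can only be solved backwards. With 40 per arm and a two-sided 5% level (sidedness is not stated for the sample size):

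- SD = 40 × √(40/2) / (1.960 + 0.842) = 63.9 MVU
- SE of the difference = 63.9 × √(2/40) = 14.28 MVU

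**3. Illustrative selection bias.** The documents give no steering rate, no MVU gap and no baseline–follow-up correlation r. Assume 10% of an arm (4 of 40) is steered, with a 40 MVU gap. The bias is 0.10 × 40 = 4 MVU, or 8 MVU if both arms are steered in opposite directions. For a bias b,

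type I error = Φ(b/SE − 1.96) + Φ(−b/SE − 1.96).

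*Selection on recorded baseline MVU.* A baseline gap d = 8 becomes r × d at follow-up. A change score carries a bias of size (1 − r)d, with SE × √(2(1 − r)).

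| r | Follow-up gap (MVU) | Unadjusted | Change from baseline |
|---|---|---|---|
| 0.3 | 2.4 | 5.3% | 6.3% |
| 0.5 | 4.0 | 5.9% | 5.9% |
| 0.7 | 5.6 | 6.8% | 5.5% |

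Adjusting for baseline MVU removes essentially all of this: 5.1% in 20,000 simulated trials at r = 0.5.

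*Selection on something the baseline recording misses.* With b = 4 the error is 5.9%, and with b = 8 it is 8.7%. Baseline adjustment shrinks the SE by √(1 − r²) but not the bias, so at r = 0.5 the figures are 6.2% and 9.9%.

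**4. BMI balance if numbering ignores BMI.** For 80 women, 40 per arm and K in the higher category, the split is hypergeometric. The probability that the arms differ by 8 or more such women is 11.7% at K = 40 and 7.3% at K = 39 or 41. Averaged over a binomial K with prevalence from 0.3 to 0.7, it is 6.7–9.3%. A split of 24 v 16 is 8/40 = 0.20. If the categories differed by an assumed 10–30 MVU, the contrast would shift by 2–6 MVU. This is chance imbalance already covered by the 5% level. It costs precision and credibility but adds no bias.

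**5. Predictability under permuted blocks.** Suppose staff always guess the arm that is behind. In a block of 2m, the expected number of correct guesses is m + (4^m / C(2m, m) − 1)/2.

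- Blocks of 4: 2 + (16/6 − 1)/2 = 2.833 of 4, or 70.8%
- Blocks of 6: 3 + (64/20 − 1)/2 = 4.1 of 6, or 68.3%
- Simulated for 80 women in two BMI categories: 70.3% (blocks of 4), 67.7% (blocks of 6), 68.8% (random mix)

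If bias scales with correct minus incorrect guesses (an assumption), the factor 2g − 1 is 0.34 to 0.42 for g = 0.67 to 0.71. The 4–8 MVU then falls to 4 × 0.34 = 1.4 up to 8 × 0.42 = 3.4 MVU, and type I error to 5.1–5.6%.

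**The case against.** The BMI label and the odd/even clause stand in one sentence, so the authors may have meant odd/even within BMI blocks, or parity as a mere code for a proper list. Predictability is therefore conditional, and non-random allocation is not proven. This stands. But the first reading is still foreseeable, and the second depends on a list that the protocol does not describe.

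The mechanism most specific to this trial, selection on visible uterine activity, leads mainly to the smaller inflation, which baseline adjustment removes. The larger figures need an unnamed factor worth as much as the whole planned effect, with both arms steered. This also stands: the figures illustrate and do not show harm.

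Delaying an approach is a weak route. Eighty women over about two years (104 weeks) is 80/104 = 0.77 per week, so waiting within one labour would seldom change the next number. Passing a woman over is more plausible, but it would breach the instruction to ask every eligible woman.

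There are further partial safeguards. Allocation follows consent, recruitment has a defined trigger, MVU is recorded for 30 minutes before dosing, and multivariable regression is planned. None of them hides a known sequence, and the analysis text does not commit to adjusting MVU for its baseline value.

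**Conclusion.** The concern holds and should be corrected before women are allocated under this rule. The only assignment rule in the protocol conflicts with its own label, and nothing else in the document supplies a random sequence, a BMI scheme or concealment. Confidence is high on that contradiction. Full predictability depends on consecutive numbering, which is the natural reading but is not stated.

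The size of any bias is unknown. Under the assumed steering it is 4–8 MVU against a planned effect of 40 MVU, with a modest rise in type I error. The severity comes from the fact that allocation is what entitles the study to be called randomised, and that it cannot be put right later.

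**What to change.** Delete the odd/even rule and keep the BMI intent. Section VI should state:

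- **Sequence:** a computer-generated permuted-block list with randomly varying block sizes (for example 4 and 6), stratified by pre-stated BMI categories.
- **Concealment:** sequentially numbered, opaque, sealed envelopes for each category, prepared by someone who does not enrol, or a central computer list.
- **Timing:** each assignment released only after consent, the eligibility check and the 30-minute baseline recording.
- **Numbering:** study numbers that carry no information about the arm.
- **Analysis:** the MVU comparison adjusted for baseline MVU and BMI category.

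If odd/even is only a code for a random list, say so and describe that list. If alternation is kept, call the study quasi-randomised in the title and in section IV.

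**Cost.** One protocol paragraph, a few hours of set-up and a holder for the list over about two years. The protocol names no non-enrolling person, so one must be found or a central list used. No extra patients or procedures are needed. With two BMI categories and blocks of up to 6, the arms could end 43 v 37. The effective size per arm is then 2 × 43 × 37/80 = 39.8, and the standard error rises by a factor of √(40/39.8) = 1.003, about 0.3%.

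**Limit.** The trial stays open-label, so staff who track each BMI category could still guess about 67–71% of assignments, against 100% under consecutive odd/even. Simple randomisation would bring this to 50% but would leave BMI to chance.

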Title: Effect of Oral Calcium Carbonate on Uterine Contractility

and Labor Outcomes: A Randomized Controlled Trial

Short Title RCT: Oral Calcium Supplementation in Labor

NCT Number: pending Protocol Date: 4-26-24

Principal Investigators

[name], DO [name] [name] [name], DO, MPH, MFM [name], MFM, MBA

Arrowhead Regional Medical Center Department of Women's Health [name] Work: [contact]/ [contact]

email: [contact]

II: Introduction/Literature review:

In the United States, cesarean delivery rates affect one in three women, with labor dystocia frequently cited as a leading cause. Labor dystocia can arise from various factors such as fetal size, positioning, pelvic structure, contractions, or maternal conditions. Clinically we can only correct the amount of uterine activity by oxytocin administration \pm amniotomy. The inability to decrease the cesarean section rate has prompted exploration for additional strategies.

One proposed method to improve uterine activity that has sparked interest in numerous social group forums is oral calcium carbonate supplementation, yet it remains largely unstudied in a clinical setting. Both calcium and carbonate components are recognized for enhancing myometrial contractility.² Physiologically, calcium plays a vital role in regulating uterine contractility throughout pregnancy.² Oxytocin triggers the release of calcium ions from intracellular stores via L-type Calcium channels within myometrial cells, inducing action potentials and thereby uterine contractility.³ During labor, there's an upsurge in calcium channel expression, facilitating uterine contractility.³ Additionally, serum calcium levels have been correlated with uterine contractility, as patients with higher calcium levels are more likely to deliver vaginally compared to those undergoing cesarean delivery.² ⁴⁻⁶

Given its potential to enhance uterine contractility and potentially reduce the need for surgical intervention, we aim to investigate the effects of calcium carbonate on uterine contractility. We hypothesized that giving calcium carbonate intrapartum can improve uterine contractility and decrease the number of cesarean deliveries.

III: Objectives: research question, purpose of the study, hypothesis

- Research questions:
 - Does calcium carbonate supplementation intrapartum improve uterine contractility, assessed by measuring Montevideo units, contraction frequency, and peak contraction strength.

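### The primary outcome is three measures over four post-dose intervals with no designated test, so the false positive chance can be about 11% to 36% rather than 5%, depending on the tests run and on assumed correlations

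*Combined protocol and SAP*

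**What the plan says.** Section VI (Study Design and analysis) gives one primary outcome, the strength of contractions, "assessed by comparing Montevideo units (MVU), frequency of contractions, and peak of the contractions 30 minutes before medication administration and at 30 minutes interval". The post-dose readings run over two hours, which makes one pre-dose window and four post-dose windows.

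The research question in section III lists the same three measures without ranking them: "assessed by measuring Montevideo units, contraction frequency, and peak contraction strength".

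The statistics paragraph of section VI offers "two-way Student's t-tests, Tukey's tests, or post hoc Student–Newman–Keuls tests as appropriate" and sets one criterion: "A p-value of less than 0.05 was considered statistically significant". It ties no test to a measure, a window or a contrast. It does not say whether the pre-dose reading is a covariate, the base of a change score, or one side of a before/after test within each arm.

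The sample size in section V (Subject recruitment) rests on MVU only: "Using a baseline Montevideo unit of 200, if we were to aim for a 20% difference with a power of 80" percent, leading to 80 women, 40 per group.

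**The concern.** A primary claim needs one defined comparison, or a stated rule for combining several. Here one test per measure, one per interval, and an arm-by-interval comparison all fit the text. If the choice is left until the data are in, a chance difference in one measure or one half-hour could carry the conclusion that calcium improves contractility. The stated purpose of the trial is to inform practice, so this matters. Under several of these readings 0.05 is not the error rate of the primary claim, and the 80% power belongs to no defined MVU summary.

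**Working it through.** **The plan's own figure.** N = 80 cannot be reproduced because no SD is given. It can only be solved backwards. The difference is 20% × 200 = 40 MVU, with 40 per arm. I assume a two-sided 0.05, since the plan does not state sidedness.

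- Normal approximation: SD = 40 × √(40/2) / (1.960 + 0.842) ≈ 63.9.
- t-based: 80% power needs a standardised difference of 0.634, so SD = 40 / 0.634 ≈ 63.1.
- Power at 40 per arm if the SD is larger: 71% at 70, 60% at 80, 42% at 100.

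**Number of tests.** Two hours in 30-minute windows gives 4 windows. Three measures × 4 windows = 12 possible post-dose comparisons.

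**Reference values if the tests were independent**, from 1 − 0.95^k:

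- k = 3: 14.3%
- k = 4: 18.5%
- k = 12: 46.0%

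**Allowing for correlation.** The tests are not independent, and the documents give no correlations. The assumptions are: MVU = frequency × peak; coefficient of variation 20% for frequency and 25% for peak; equal correlation ρ between any two intervals in the same woman; 40 per arm; no treatment effect; 20,000 simulated trials per setting. The chance of at least one p < 0.05, with frequency and peak uncorrelated, is:

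| Reading of the plan | ρ = 0.4 | 0.6 | 0.8 | 0.9 |
|---|---|---|---|---|
| Three two-hour means, unadjusted | 11.5% | 11.6% | 11.5% | 11.6% |
| MVU alone at four intervals | 16.9% | 14.3% | 11.4% | 9.5% |
| All 12 interval tests | 35.5% | 30.9% | 24.8% | 20.8% |
| Tukey on 8 arm-by-interval cells, over three measures | 6.7% | 5.3% | 3.7% | 2.5% |
| One MVU mean, adjusted for baseline | 5.0% | 5.1% | 4.8% | 4.7% |

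Letting the frequency–peak correlation run from −0.3 to 0.3 gives 10.6–12.2% for the three means and 19.4–36.2% for the 12 tests.

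**Sensitivity.** A separate simulation used interval correlations of 0.3 to 0.9, either equal or decaying with time, and a frequency–peak correlation of 0 or 0.3. It gave 10–12% for three means, 9–18% for MVU at four intervals, 19–38% for 12 post-dose tests, and 27–34% for 12 tests on change from baseline.

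**Tukey and Student–Newman–Keuls.** With two arms at one interval, both reduce to a t-test. The Tukey row above treats a woman's four readings as independent cells, which makes it conservative (1–3% per measure). A version that respects the within-woman correlation could sit near 5% per measure, and about 10–14% over the three. Student–Newman–Keuls on the eight cells was not simulated.

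**Adjusting instead of choosing.** With SD 63.9 and 40 per arm, Bonferroni lowers the power of each test from 80% to 66% for 3 tests, 62% for 4 and 47% for 12. Keeping 80% would need 54, 57 or 71 per arm.

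**The case against.** The best defence is that MVU is the lead measure in all but name. The trial is sized on it, the pressure catheter is required so that it can be measured accurately, and it is listed first each time. This narrows the ambiguity but does not remove it: section VI gives frequency and peak the same primary status, and MVU alone at four unadjusted intervals still gives about 9–17%.

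A second defence is that the plan never proposes 12 unadjusted t-tests and does name multiple-comparison procedures. That is fair: 36% is the upper end, not a forecast, and one Tukey implementation would leave little or no inflation. But the plan lists Tukey as one option among several, and neither procedure adjusts across three different measures.

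Third, all the percentages above 5% rest on assumed correlations. This stands, and they should be read as ranges. The absence of a designated test needs no assumption.

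Fourth, a two-hour mean is not the only valid choice, and it could dilute a short or delayed effect. This also stands. One named interval or a fixed testing sequence would control the error too. The mean is suggested because it uses all the readings and the measure on which the trial was sized.

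Finally, the statistics paragraph is partly in the past tense, so the documents do not establish that outcome data are still unseen.

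**Conclusion.** The concern holds and should be fixed before outcome data are seen. The primary claim has no defined test, so neither the 5% error nor the 80% power attaches to anything specific. Under the assumed correlations (0.4–0.9 between intervals, −0.3 to 0.3 between frequency and peak), the chance of a false positive is 11–12% with one unadjusted test per measure, 10–17% with MVU at four intervals, and 19–36% with all 12 tests. It would be about 5% for a single pre-chosen MVU test, and 2–7% under one form of Tukey. The text permits each of these and commits to none. The missing SD is a separate gap and does not affect these error rates.

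**What to change.** Before outcome data are seen, and with a dated record that this is so:

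- Name one primary endpoint: mean MVU over the two hours after time zero, compared between arms once at two-sided 0.05, adjusted for the pre-dose 30-minute MVU already collected.
- State how a woman who delivers before two hours, or whose readings are otherwise incomplete, enters that mean.
- Make frequency, peak and interval-specific values secondary. Report them with confidence intervals from a repeated-measures model with a patient effect, in place of the open list of tests.
- State the SD assumed for the chosen MVU summary.

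A separate but related point: the windows are anchored to medication administration, yet the plan has "Control group: no medication". Define one reference time that is recorded in both arms.

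The cost is mostly wording. N stays at 80, but 80% power for 40 MVU holds only if the SD of the chosen summary, after baseline adjustment, is about 63 or less. A reference time for controls is a small added data item. The downside is that frequency, peak or a single interval can no longer carry the primary claim. A short or delayed effect would be diluted in the mean, though the interval-specific secondary estimates would still show it.
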